6.3.4 SCAR-Q Appearance Scale (Subject)

The SCAR-Q is a patient-reported outcome instrument designed to measure outcomes specific to any type of scar. This instrument has subscales for scar appearance, psychosocial impact and scar symptoms. Least-square means and confidence intervals will be calculated for each scale and subscale using generalized linear models with lesion size included as a fixed effect.

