An initial NSR BCC feasibility study (NP-BC-005) demonstrated that the NPS Device was successful in treating basal cell carcinoma lesions without safety concerns. A portion of 1-2 biopsy confirmed BCC lesions were treated in the 48 Subjects enrolled. 48 NPS treated areas were evaluated by a board certified dermatopathologist. There was no presence of BCC located within the NPS treated area in all samples analyzed for superficial and nodular low risk BCC lesions. The treated areas showed favorable healing clinically.

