3.0 PROTOCOL

3.1 Study Objectives

The primary objectives of this study are to evaluate the safety and effectiveness of the CellFX System in adults with low-risk basal cell carcinoma. Table 1 below reflects the study endpoints associated with the two objectives.

Table 1. Study Objectives and Endpoints

Objectives	Endpoints
Safety To evaluate the safety of the CellFX System in adults with low-risk basal cell carcinoma	Primary: 
 • No serious adverse events related to CellFX Treatment or Procedure Secondary: 
 • Local Skin Reactions (Investigator) • Procedural pain assessment (Subject)
Effectiveness To evaluate the effectiveness of the CellFX System in adults with low-risk basal cell carcinoma	Primary: 
 • Complete histological clearance of the target lesion on microscopic evaluation of hematoxylin and eosin stains Secondary: 
 • Visible/clinical clearance of the target lesion by clinical/dermatoscopic evaluation • Partial response of the study lesion as assessed by WHO criteria ($\geq 50\%$ decrease in the product of the longest perpendicular diameters of each target lesion) • SCAR-Q Appearance Scale (Subject) • Manchester Scar Scale (Investigator) • Healing assessment questions (Investigator)

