6.3.5 Manchester Scar Scale (Investigator)

The Manchester Scar Scale evaluates the following five characteristics of scar: color (score: 1–4), distortion (score: 1–4), contour (score: 1–4), texture (score: 1–4), and transparency (score: 1–2). The distribution of responses will be summarized for each characteristic. Least-square means and confidence intervals will be calculated for the total score using generalized linear models with treatment lesion size included as a fixed effect.

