6.3.6 Healing assessment questions (Investigator)

The following assessment questions will be asked on the Day 60 post-NPS treatment visit prior to surgical excision as well as on the Day 60 post-surgical excision visit:

- a. Is the healing pattern cosmetically acceptable? (yes, no)
- b. How likely is a scar? (1 = unlikely, 2 = possible, 3 = probable)
- c. Once healed, how do you anticipate the treated area will look compared to curettage and desiccation? (1 = better, 2 = the same, 3 = worse)
- d. Once healed, how do you anticipate the treated area will look compared to surgical

excision? (1 = better, 2 = the same, 3 = worse)
The distribution of responses will be summarized for each question.

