6.4.2 Investigator Local Skin Reaction Assessment

[figure not shown]
The Investigator will perform clinical assessments on the local skin reaction of the treatment area based on the following characteristics: presence and severity of erythema, edema, exudate, eschar, peeling scaling, bleeding, ulceration, scarring, and pigmentary changes. Assessment will be based on a validated 5-point scale: None, Mild, Moderate, Moderate to Severe, Severe. The wound healing characteristics will be assessed by the investigator at the 14-Day and 60-Days Post-NPS visits. The 3-Day, 7-Day, and 30-Days Post-NPS visits are optional in-office and will be summarized separately and included as a descriptive analysis. The rate of each event individually and a composite of any of these events will be calculated for each treated lesion area. The number and proportion of lesions with any reporting of any erythema, edema, exudate, eschar, peeling scaling, bleeding, ulceration, scarring, or pigmentary changes (regardless of severity) will be summarized by time-point.

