6.10 Exploratory Analysis

Exploratory analysis may be performed to compare the different BCC subtypes. Wound healing characteristics for the post-excision area will also be assessed and compared to the wound healing characteristics post-NPS.

Exploratory analysis may be performed for dermatologic similarities of skin type based on anatomic subcategories:

- Sun-exposed limbs
- Non-sun exposed limbs
- Torso

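### The SCAR-Q and Manchester models (6.3.4, 6.3.5) make no allowance for two lesions in one subject and do not say which visit gives the CellFX result

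*Combined protocol and SAP*

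**What the plan says.** Table 1 (section 3.1) lists the SCAR-Q Appearance Scale, the Manchester Scar Scale and the investigator's healing questions as secondary endpoints under the objective "To evaluate the effectiveness of the CellFX System in adults with low-risk basal cell carcinoma".

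Table 3 and sections 4.10 and 4.13 collect all three for each treatment area at two visits. Visit 6 comes 60 days after CellFX and scores the area before it is excised. Visit 9 comes 60 days after excision. Section 3.2 allows one or two lesions per subject.

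The analysis text reads as follows.

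- **SCAR-Q (6.3.4):** least-square means and intervals are "calculated for each scale and subscale using generalized linear models with lesion size included as a fixed effect".
- **Manchester (6.3.5):** they are "calculated for the total score using generalized linear models with treatment lesion size included as a fixed effect".
- **Healing questions (6.3.6):** they are asked "prior to surgical excision as well as on the Day 60 post-surgical excision visit". The one analysis sentence gives a distribution per question and does not mention visit.

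Elsewhere the plan is more specific. Section 6.3.1 names a repeated-measures mixed model with baseline lesion size, 6.3.3 fixes day 60 after CellFX, and local skin reactions in 6.4.2 "will be summarized by time-point".

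**The concern.** Two scores from one subject share the patient's healing and the same rater: the subject for SCAR-Q, the site investigator for Manchester. They are likely to be positively correlated. A model whose only stated term is lesion size treats them as separate pieces of information and overstates precision. Section 6.1 plans no inferential tests, so estimates and intervals are this study's statistical output, and section 1.6 says the data will be used to design a pivotal study.

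The missing visit is a separate gap. The Visit 6 score describes skin healed after CellFX. By Visit 9 that skin has been removed and the score describes a surgical scar. The text does not say which of the two is the CellFX result, so the choice could be made after both are known.

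Three smaller gaps sit in the same sections:

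- Table 3 schedules lesion measurement at Visits 1 and 6. Unlike 6.3.1, sections 6.3.4 and 6.3.5 do not say that the covariate is the baseline measurement.
- Healing question d compares the treated area with surgical excision, which is circular at Visit 9.
- Section 6.3.4 describes three SCAR-Q subscales (appearance, psychosocial impact, symptoms) and plans estimates for each. Tables 1 and 3 and sections 4.10 and 4.13 schedule the Appearance Scale alone.

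**Working it through.** The plan gives no figure to reproduce, because section 6.5 sets the sample size without a power or precision target. The check is how far a 95% interval falls short when two lesions in one subject are treated as independent.

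**Inputs from the documents.** At most 30 subjects (3.5, 6.5); one or two lesions each (3.2).

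**Inputs assumed.** The documents give neither the number of two-lesion subjects nor the correlation. Let k of the 30 subjects have two lesions, with k = 0, 3, 6 or 30, and let the within-subject correlation ρ be 0.2 to 0.6.

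**Formula.** With N = 30 + k lesions of equal variance σ², the variance of the lesion mean at one visit is (σ²/N²)(N + 2kρ). An independence model uses about σ²/N. The ratio is

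F = 1 + 2kρ/N

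and the nominal 95% interval then covers with probability about 2Φ(1.96/√F) − 1.

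**Example.** For k = 3 and ρ = 0.6: N = 33, F = 1 + 2×3×0.6/33 = 1.109, √F = 1.053, 1.96/1.053 = 1.861, coverage 93.7%.

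**Visit 6 analysed alone**

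| Two-lesion subjects (k) | Lesions (N) | F, ρ = 0.2 / 0.4 / 0.6 | Coverage, ρ = 0.2 / 0.4 / 0.6 |
|---|---|---|---|
| 0 | 30 | 1.00 / 1.00 / 1.00 | 95.0% / 95.0% / 95.0% |
| 3 | 33 | 1.036 / 1.073 / 1.109 | 94.6% / 94.2% / 93.7% |
| 6 | 36 | 1.067 / 1.133 / 1.200 | 94.2% / 93.4% / 92.6% |
| 30 | 60 | 1.2 / 1.4 / 1.6 | 92.6% / 90.2% / 87.9% |

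**Which row is likely.** Section 1.5 describes an earlier feasibility study that also treated one or two lesions per subject. In its 48 subjects, "48 NPS treated areas were evaluated by a board certified dermatopathologist". That is one area per subject on average and points to the upper rows.

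**Does the remedy work?** This was simulated at Visit 6 with lesion size as covariate: 2,000 runs per case, Monte Carlo standard error about 0.5 percentage points.

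| k | Independence model, ρ = 0.2 / 0.6 | Cluster-robust SE, t on 29 df | Subject random intercept | Cluster-robust width relative to independence model |
|---|---|---|---|---|
| 3 | 94.2% / 94.4% | 94.8% / 95.4% | 95.0% / 95.4% | 1.02 / 1.05 |
| 6 | 94.8% / 92.3% | 95.6% / 94.0% | 95.8% / 94.4% | 1.03 / 1.09 |
| 30 | 92.3% / 86.8% | 94.9% / 94.4% | 95.4% / 94.5% | 1.11 / 1.29 |

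Both remedies hold coverage near 95%. With few two-lesion subjects the random-intercept variance is often estimated at zero (37% of runs at k = 3, ρ = 0.2), without loss of coverage.

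**The case against.** **The effect is negligible at plausible lesion counts.** With 3 two-lesion subjects the shortfall is 0.4 to 1.3 percentage points by formula, and at that count the simulation cannot separate it from noise. No test depends on it. This stands as a limit on weight. It does not justify a model that ignores a feature the design allows, when the correct one costs nothing in data.

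**The CellFX visit can be worked out.** Table 1 ties the scales to CellFX effectiveness, 4.10 scores them before excision, and the missing-data text in 6.9 refers to 60-day post-treatment results. These point to Visit 6, but none fixes the analysis visit for the scar scales, and 6.3.6 itself uses the label Day 60 for both visits. The gap narrows but stays open.

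**Stronger reading: the plan pools both visits.** A reader might infer that one model over both visits will average two different scars. With equal numbers at each visit that would shift the mean by half the visit difference, for example 1 point for an assumed 2-point difference on the Manchester total (range 5 to 18: four items scored 1–4 and one scored 1–2). The documents do not support the inference. They do not exclude pooling, but nowhere state it, and 6.10 keeps the two kinds of skin apart: "Wound healing characteristics for the post-excision area will also be assessed and compared to the wound healing characteristics post-NPS". A sensible analyst would probably report by visit.

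**Question c.** A reader might want it dropped at Visit 9 along with d. It asks "Once healed, how do you anticipate the treated area will look compared to curettage and desiccation". Section 4.13 still calls the site a treatment area after excision, so c can be answered for the excision scar and may stay. Only d loses its meaning.

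**Subscales.** The case report forms are a separate attachment and were not seen. The mismatch is real, but which side is right cannot be settled from these documents.

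**Scope.** Sections 6.2 and 6.3.3 are equally silent on two lesions per subject. That is fair, and it argues for one rule placed centrally.

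**Conclusion.** The point holds as a cheap improvement of minor weight. As written, the scar-scale models ignore within-subject correlation, and their intervals are somewhat too narrow if any subject has two lesions. Coverage at Visit 6 is unaffected with one lesion each, about 94.6% to 93.7% with 3 of 30 two-lesion subjects, and no lower than 87.9% under the assumptions used. Those assumptions are a common correlation of 0.2 to 0.6, equally weighted lesions, and two-lesion counts that the documents do not give.

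Independently of the arithmetic, the plan leaves unstated which visit supplies the CellFX result for SCAR-Q and Manchester, and it does not say that the healing questions are tabulated by visit.

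Nothing here shows that visits will be pooled or that a study conclusion is wrong.

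**What to change.** - **6.3.4 and 6.3.5:** name the Visit 6 pre-excision score as the CellFX endpoint. Estimate its least-square mean and interval with baseline lesion size as covariate and clustering by subject, using cluster-robust standard errors (GEE) or a subject random intercept. Report Visit 9 separately as the post-excision scar.
- **Visit 9 minus Visit 6, if shown:** keep it descriptive. State that it is not a clean device-versus-surgery comparison, because the order is fixed and the excised skin had already been treated.
- **6.1:** preferably state the clustering rule once here, so that it also covers the other lesion-level estimates.
- **6.3.6:** tabulate responses by visit, and state that question d at Visit 9 is not read as a CellFX result. Question c may stay.
- **6.3.4 against Tables 1 and 3, 4.10 and 4.13:** reconcile which SCAR-Q scales are collected and analysed.

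The cost is a few sentences, with no new data and no change in sample size. Intervals widen by about 2% to 5% with 3 two-lesion subjects, 3% to 9% with 6, and 11% to 29% if all 30 have two.

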6.3.5 Manchester Scar Scale (Investigator)

The Manchester Scar Scale evaluates the following five characteristics of scar: color (score: 1–4), distortion (score: 1–4), contour (score: 1–4), texture (score: 1–4), and transparency (score: 1–2). The distribution of responses will be summarized for each characteristic. Least-square means and confidence intervals will be calculated for the total score using generalized linear models with treatment lesion size included as a fixed effect.

6.3.6 Healing assessment questions (Investigator)

The following assessment questions will be asked on the Day 60 post-NPS treatment visit prior to surgical excision as well as on the Day 60 post-surgical excision visit:

- a. Is the healing pattern cosmetically acceptable? (yes, no)
- b. How likely is a scar? (1 = unlikely, 2 = possible, 3 = probable)
- c. Once healed, how do you anticipate the treated area will look compared to curettage and desiccation? (1 = better, 2 = the same, 3 = worse)
- d. Once healed, how do you anticipate the treated area will look compared to surgical

excision? (1 = better, 2 = the same, 3 = worse)
The distribution of responses will be summarized for each question.

6.4 Safety Endpoints

Unless otherwise noted, the safety population will be used to assess safety endpoints.

6.4.1 Primary Safety Endpoint

The primary safety endpoint is the incidence of any serious AEs or complications associated with the application of NPS (procedure and treatment). Information about AEs and complications will be solicited by site investigators at scheduled follow-up visits. The count and proportion with the primary safety endpoint will be calculated along with a 95% confidence interval. Adverse events and complications will also be summarized by MedDRA preferred term.

6.4.2 Investigator Local Skin Reaction Assessment

[figure not shown]
The Investigator will perform clinical assessments on the local skin reaction of the treatment area based on the following characteristics: presence and severity of erythema, edema, exudate, eschar, peeling scaling, bleeding, ulceration, scarring, and pigmentary changes. Assessment will be based on a validated 5-point scale: None, Mild, Moderate, Moderate to Severe, Severe. The wound healing characteristics will be assessed by the investigator at the 14-Day and 60-Days Post-NPS visits. The 3-Day, 7-Day, and 30-Days Post-NPS visits are optional in-office and will be summarized separately and included as a descriptive analysis. The rate of each event individually and a composite of any of these events will be calculated for each treated lesion area. The number and proportion of lesions with any reporting of any erythema, edema, exudate, eschar, peeling scaling, bleeding, ulceration, scarring, or pigmentary changes (regardless of severity) will be summarized by time-point.

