4.2.1 Inclusion Criteria

Candidates for this study must meet **ALL** the following criteria:

1. Subject is at least 22 and no older than 85 years of age.
2. Subject has 1-2 primary, non-recurrent, superficial, or nodular visible basal cell carcinoma lesion up to 1.5 cm in size with well-defined borders that has been verified by biopsy.
3. Lesion(s) is appropriate for full linear excision with 5 mm margins.
4. Subject is capable of giving signed informed consent, which includes compliance with the requirements and restrictions listed in the ICF and in this protocol.

5. Subject gives voluntary, written informed consent to participate in this clinical investigation and from whom consent has been obtained.
6. Subject is willing to have BCC lesion(s) treated in a single treatment session and must comply with all study procedures including follow-up visits.
7. Subject consents to have photographs taken of the BCC lesion(s).
8. Subject agrees to refrain from using all other lesion removal products or treatments (topical medication including over-the-counter medications or treatments from PI or another physician) during the study period.
9. Subject agrees to refrain from prolonged sun exposure of the treatment area during the study period.

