4.5.3 CellFX Treatment Procedure

- 1-2 clinically diagnosed BCC lesion(s) that meet the study criteria will be selected by the treating investigator. The identified lesion(s) will be labeled.
- Baseline photographs will be taken (prior to use of analgesic for pain management and prior to tattooing).
- Baseline clinical measurements of the BCC lesion(s) shall be taken
- The site investigator will perform a baseline lesion(s) assessment.
- A template will be applied to the skin and used to map out the treatment application.
- A tattoo (4 marks) will be applied within the area designated for excision to mark the treatment zones for the purpose of identifying the treatment area during evaluation.
- An analgesic for pain management, such as local injection of lidocaine, will be administered to the selected study lesion area(s).
- Each study lesion will be treated with the CellFX system per Table 2 according to the treatment tips utilized.
- The total number of treatment cycles with the CellFX system will be recorded.
- The subject will be asked to rate his/her pain immediately after the treatment session for each lesion treated with the CellFX system by using a numerical rating score, depicted in Figure 4.
- Post-procedure lesion assessment will be performed by the investigator.
- Post-procedure photographic images of each selected lesion will be taken.
- A light bandage and/or any physician recommended dressing may be applied before the subject leaves.
- Any adverse events will be identified and documented.

4.6 3-Day Follow-up Visit (Visit 2)

- This visit may be performed in-office or as a telemedicine visit.
- Photographic images of each study lesion will be taken. Photographs are not required if the visit is not performed in-office.
- All lesions will be examined and clinically assessed by the site investigator. If the visit is not performed in-office, clinical assessment is not required.
- A light bandage and/or any physician recommended dressing may be applied post-evaluation.
- Any adverse events will be identified and documented. If the visit is not performed in office, the clinical site must inquire regarding any adverse events either by phone call, text, e-mail or video conference.

4.7 7-Day Follow-up Visit (Visit 3)

- This visit may be performed in-office or as a telemedicine visit.
- Photographic images of each study lesion will be taken. Photographs are not required if the visit is not performed in-office.

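### Local skin reactions are graded on five levels but summarised only as present or absent, without the pre-procedure assessment, so mild and severe signs, and new and pre-existing ones, are not separated

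*Combined protocol and SAP*

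**What the plan says.** Table 1 in Section 3.1 lists investigator-rated local skin reactions as a secondary safety endpoint. Section 6.4.2 says how they are rated and summarised.

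- **What is rated:** "presence and severity of erythema, edema, exudate, eschar, peeling scaling, bleeding, ulceration, scarring, and pigmentary changes", which is nine signs.
- **Scale:** "Assessment will be based on a validated 5-point scale: None, Mild, Moderate, Moderate to Severe, Severe".
- **When:** "The wound healing characteristics will be assessed by the investigator at the 14-Day and 60-Days Post-NPS visits". The Day 3, 7 and 30 visits are optional in-office visits and are summarised separately. No pre-procedure time is named.
- **Summaries:** "The rate of each event individually and a composite of any of these events will be calculated for each treated lesion area". In addition, the number and proportion of lesions with any of the nine signs, "regardless of severity) will be summarized by time-point".

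Two other places bear on this. Inclusion criterion 2 (Section 4.2.1) requires a visible lesion "that has been verified by biopsy". Section 4.5.3 says of Visit 1: "The site investigator will perform a baseline lesion(s) assessment". Table 3, footnote a, places the Visit 1 lesion assessment both before and after the procedure. Neither place names the scale used.

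**The concern.** The treated skin is not normal at the start. A visible BCC that has been biopsied may already show redness, scaling, ulceration, a scar or altered pigment. A rule that counts any sign at any visit does not ask whether the sign was there before treatment, although an assessment that could answer the question is scheduled.

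The rule also asks only whether a sign is present. The grades are recorded, but no specified summary for this endpoint reports them. Other sections do not fill the gap. Section 8.0 collects severity for adverse events, but Section 6.4.1 summarises them by MedDRA preferred term. The pain endpoint in Section 6.4.3, by contrast, is grouped into severity categories and tabulated.

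At stake is how well a named safety endpoint can be read. There is no control arm, so the pre-procedure state of the same lesion is the natural reference. Section 1.6 says that the data will help to choose the treatment and design a pivotal study.

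**Working it through.** **1. Plan's own figure.** There is none to reproduce. The documents give no expected reaction rate, background rate or precision target for this endpoint. The check is therefore of the counting rule; every rate below is an assumption.

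**2. Inputs from the documents.** Nine signs and five grades (Section 6.4.2); at most 30 participants (Section 6.5) with 1-2 lesions each (Section 3.2), so at most 60 lesions.

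**3. Severity.** Suppose that every lesion shows at least one sign. If all grades are Mild, the composite is 30/30 = 100%. If all are Severe, it is again 30/30 = 100%. The exact 95% interval is 88.4-100% for 30/30, or 94.0-100% for 60/60 ignoring correlation within participants. It is identical in the two cases. The per-sign rates have the same limit: they show which sign occurred, not how bad it was.

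**4. Baseline.** Take one sign on one lesion, graded Mild before treatment and Mild at Day 60, and another graded None and then Mild. Each counts once at Day 60. Against the pre-procedure grade, the first counts 0 and the second 1.

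A Day 0 column alone would not separate them. Suppose that 15 of 30 lesions have the sign at Day 0 and 15 of 30 at Day 60. Both columns read 50% whether the same 15 lesions are affected (new signs 0/30) or the other 15 are (new signs 15/30). Only a within-lesion shift distinguishes these.

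**5. Possible size for the composite.** Let q be the assumed probability that a given sign is present for reasons other than the device, equal for all nine signs.

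- If the signs are independent, the composite is 1 - (1 - q)^9.
- If they overlap completely, it is q.

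| Assumed q | Full overlap | Independent |
|---|---|---|
| 5% | 5% | 1 - 0.95^9 = 37% |
| 10% | 10% | 1 - 0.90^9 = 61% |
| 20% | 20% | 1 - 0.80^9 = 87% |

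Positively associated signs fall between the two columns. A common q is a simplification: before treatment, bleeding or exudate need not be as frequent as scarring.

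**6. Effect on the reading.** Let b be the background any-sign rate and t the true new-onset rate, independent of it, with background signs persisting to the visit. The any-grade rate is b + (1 - b)t.

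- b = 0.5: t = 10% shows as 0.5 + 0.5 × 0.1 = 55%, and t = 50% as 0.5 + 0.5 × 0.5 = 75%.
- b = 0.8: t = 10% shows as 0.8 + 0.2 × 0.1 = 82%, and t = 50% as 0.8 + 0.2 × 0.5 = 90%.

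The higher the background, the less the any-grade rate responds to what the device does. If treatment removes the tumour's own signs, the background at Day 60 is lower and the distortion smaller.

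**The case against.** The case on the other side has substance.

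- A reader might infer that **severity is thrown away**. The documents do not support that. Grades are recorded for every sign, and Section 6.1 promises counts and percentages for categorical variables, which would permit a grade table. What stands is that none is specified for this endpoint.
- A reader might infer that **comparable baseline grades are already in hand**. Neither Table 3 nor Section 4.5.3 gives a scale for the Visit 1 assessment. Section 6.4.2 names the five-point scale but ties it only to post-treatment visits. The case report forms are a separate attachment. The scale has to be confirmed.
- **The composite is not the whole analysis.** Per-sign rates are also planned and would separate, say, ulceration from erythema. That limits the loss without restoring grade or change.
- **Pre-existing features might not be scored.** Section 6.4.2 asks about the local skin reaction, and rating instructions not in these documents could tell investigators to ignore old scars. So pre-existing signs can count; the documents do not show that they will, or how often.
- **Counting everything is conservative for safety.** If tumour scaling is replaced by device-caused scaling of equal grade, a new-or-worse rule misses it. This is a good reason not to replace the any-grade count.
- **The endpoint is descriptive and secondary.** Serious adverse events, adverse-event severity, the Manchester Scar Scale and the healing questions also inform safety and healing. A reader might infer that the device's safety cannot be judged, or that a comparison of energy settings is spoiled. Section 6 plans no such comparison, and the other data remain.

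**Conclusion.** The point holds as a gap in the specified summaries. Followed as written, Section 6.4.2 cannot show whether reactions were mild or severe, or whether a sign was new, worse or already present on the lesion. This follows from the counting rule and needs no assumed rate.

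The size cannot be computed from the documents. Under one common assumed background per sign of 5%, 10% or 20%, the background composite lies in 5-37%, 10-61% or 20-87%, from complete overlap to independence. Quoting only the upper ends would overstate the case. The consequence is confined to a descriptive secondary safety endpoint in a single-arm study of up to 30 participants. It is a cheap and worthwhile improvement; it does not undermine the study's safety assessment.

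**What to change.** In Section 6.4.2, keep the per-sign rates and the any-grade count, and add for each sign and visit:

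1. the distribution of lesions over the five grades;
2. the shift from the Visit 1 pre-procedure grade of the same lesion, with the proportion of lesions whose sign is new or worse than before the procedure, overall and at moderate or worse.

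In Section 4.5.3 or Table 3, state that the pre-procedure assessment at Visit 1 grades all nine signs on the same five-point scale.

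The cost is a few more tables and, if Visit 1 does not already use the scale, a small clarification of the case report form, which has to be in place before lesions are treated. The new-or-worse proportion can miss a device-caused sign of the same grade as baseline, so the two counts should be reported side by side.
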